4.3.2 OPEN Questions?

Further instructional information on OPEN is provided on the OPEN link of the CTSU website at <https://www.ctsu.org> or at <https://open.ctsu.org>. For any additional questions contact the CTSU Help Desk at [REDACTED] or [contact].

5 TREATMENT PLAN

Treatment will generally be administered on an outpatient basis. Reported adverse events and potential risks are described in Section [7](#). Appropriate dose modifications are described in Section [6](#). No investigational or commercial agents or therapies other than those described below may be administered with the intent to treat the patient's tumor.

Timing of protocol therapy administration and response assessment studies are based on schedules derived from the experimental design or on established standards of care. Minor unavoidable departures (up to 72 hours) from protocol directed therapy and/or disease evaluations for valid clinical, patient and family logistical, or facility, procedure and/or anesthesia scheduling issues are acceptable.

5.1 Agent Administration

5.1.1 APX005M (CD40 agonistic mAb)

APX005M dosing will begin at 0.1 mg/kg, which is one dose level below the adult recommended phase 2 dose. For APX005M, both 1 mg/kg and 0.6 mg/kg were explored in adult participants, and the adverse events at 0.6 mg/kg were manageable and reversible. The APX005M dose will be increased in subsequent cohorts until the MTD is reached or until dose level 3 is complete without MTD being defined (

Table 2). No inpatient dose escalation will be permitted on the protocol. Only DLTs observed during the dose-finding period (the first 2 courses, i.e., the first 6 weeks of treatment) will be used to guide dose escalation. Dose escalation will be governed by the statistical design as described in section 13 of the protocol.

Table 2

Dose Escalation Schedule		
Dose Level	Dose of APX005M (mg/kg, IV, Q3 weeks)	round final dose to
0	0.03 mg/kg	2 decimals
1* (starting dose level)	0.1 mg/kg	1 decimal
2	0.3 mg/kg	1 decimal
2.5	0.45 mg/kg	1 decimal
3	0.6 mg/kg	1 decimal
Note: Dose level 2.5 will only be studied if dose level 3 is deemed to be too toxic.		

Subjects will be assigned a dose level at the time of enrollment. APX005M will be administered at the assigned dose level on Day 1 of each course 21 day. Patients may continue to receive APX005M for 36 courses (approximately 2 years) or until disease progression, unacceptable toxicity or death, whichever occurs first. Delays between courses for reasons other than toxicity may occasionally occur however dosing should follow the treatment plan as closely as possible.

Dosing should be adjusted based on weight (kg) calculated at the beginning of each course of therapy. The dose may be prescribed using the weight that was determined at the prior visit. However, if the current weight is $\geq 5\%$ different from the prior weight, the prescription should be revised.

Accrual to Stratum 1 was completed as of May 14, 2020. Dose level 3 (0.6mg/kg) was determined to be the recommended phase 2 dose for Stratum 1. The starting dose for Stratum 2 (the DIPG cohort) was set to be one dose level below the RP2D determined in the non-DIPG patients (Stratum 1) (also see Section 13.1.3). Therefore, accrual to Stratum 2 was initiated at dose level 2 (0.3mg/kg). Accrual to Stratum 2 remains open at the time of this amendment.

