5.1.3 Criteria to Start Subsequent Courses

A course may be repeated every 3 weeks if the patient has at least stable disease, all drug-related toxicities return to baseline or \leq Grade 1 (excluding alopecia and Grade 2 fatigue) and has again met laboratory parameters as defined in Section 3.1.9. If a patient does not meet these parameters at the end of the treatment course then APX005M should be held until parameters meet the eligibility criteria.

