5.3.6 Neurosurgical or other surgical procedures

If a neurosurgical procedure or other surgical procedure is required for a reason other than tumor progression (i.e. the onset of hydrocephalus), these procedures should be documented, but will not constitute criteria for declaring the patient “off therapy”. APX005M should be held until the patient is clinically stable and has recovered from the acute effects of surgery.

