6 DOSING DELAYS/DOSE MODIFICATION

If a subject fails to meet criteria to start subsequent course (section 5.1.3) then treatment with investigational product should be delayed and the subject should be re-evaluated weekly. Any subject who fails to recover from a disease or treatment-related toxicity to baseline or \leq Grade 1 (except alopecia and Grade 2 fatigue) within 2 weeks of scheduled retreatment, or within 1 week of scheduled retreatment if toxicity is related to cytokine release, should discontinue the investigational product.

Subjects requiring more than 2 dose reductions, or dose reduction below dose level 0, must discontinue the investigational product.

Management of suspected adverse drug reactions may require temporary interruption and/or dose reduction of APX005M. If a subject experiences several toxicities, the recommended dose adjustment should be based on the highest grade toxicity. All dose reductions for APX005M, if required, will follow the dose levels defined in

Table 2.

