11 MEASUREMENT OF EFFECT

Although the clinical benefit of APX005M has not yet been established, the intent of offering this treatment is to provide a possible therapeutic benefit, and thus the patient will be carefully monitored for tumor response and symptom relief in addition to safety and tolerability. Patients with measurable disease will be assessed by standard criteria. For the purposes of this study, patients should have MRI scan within 3 weeks prior to enrollment, at the end of course 2, every 3 courses through course 14, and then every 4 courses till the end of therapy, and at the time of disease progression or completion of treatment. In addition to a baseline scan, confirmatory scans will also be obtained 9 weeks following initial documentation of an objective response.

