*** Consideration for possible pseudo-progression**

For patients showing possible radiographic evidence of tumor progression on MRI during the first 6 months after initiation of APX005M (on required MRI studies performed at the end of Course 2, 5, 8), the treating physician will have the option of allowing the patient to remain on study, continuing protocol therapy, and repeating disease reassessment in 4-6 weeks. Provided that the patient does not show clinical deterioration consistent with tumor progression, has been on a stable or declining dose of steroids, and the subsequent MRI demonstrates tumor regression or stable disease, then the patient will remain on study and continue protocol therapy, and the frequency of subsequent MRI will revert to pre-specified intervals. If the repeat MRI after 4-6 weeks shows disease progression, rather than pseudo-progression, then the time of progression will be the date of the initial MRI, not the follow up scan. The addition of steroids is allowed, at the time of suspected pseudo-progression, as long as the patient can be maintained on a decreasing dose.

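### Routine MRIs are timed by treatment course, so dosing delays move later scans and can postpone the recorded date of scan-detected progression in DIPG

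*Combined protocol and SAP*

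**What the plan says.** **Scan timing.** Section 11 places routine on-treatment MRIs "at the end of course 2, every 3 courses through course 14, and then every 4 courses till the end of therapy", and Sections 9.2 and 10 (footnote E) repeat this. A scan is also due "and at the time of disease progression or completion of treatment". Courses last three weeks (5.1.1): "APX005M will be administered at the assigned dose level on Day 1 of each course 21 day".

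**Delays.**
- Non-toxicity reasons (5.1.1): "Delays between courses for reasons other than toxicity may occasionally occur however dosing should follow the treatment plan as closely as possible". No maximum is given.
- Surgery (5.3.6): "APX005M should be held until the patient is clinically stable and has recovered from the acute effects of surgery". No maximum is given.
- Unmet retreatment criteria (5.1.3): "APX005M should be held until parameters meet the eligibility criteria". This sentence has no limit, but Section 6 takes up patients who fail 5.1.3. It requires weekly re-evaluation and stops the drug in anyone who has not recovered from toxicity "within 2 weeks of scheduled retreatment, or within 1 week of scheduled retreatment if toxicity is related to cytokine release".
- Logistics (Section 5): minor departures of up to 72 hours are accepted, for treatment and for disease evaluations.

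**Endpoint.** PFS runs from the start of treatment to the earliest documented progression or death (11.3.5), with no rule for late or off-schedule scans. Progression includes neurologic worsening as well as growth on imaging (11.3.4). The pseudo-progression option applies "during the first 6 months after initiation of APX005M (on required MRI studies performed at the end of Course 2, 5, 8". Section 1.2 makes DIPG response, duration of response, PFS and OS a secondary objective. Section 13.3 reports PFS descriptively and calls the analyses exploratory.

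**The concern.** A patient on hold does not advance through courses, so no routine MRI falls due until dosing resumes. The weekly re-evaluation in Section 6 specifies no imaging. The 72-hour allowance does not restore the calendar, because the due date itself moves with the course. Dating confirmed progression back to the first suspicious MRI (11.3.4) does not help when that MRI was itself late.

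How often a patient is imaged therefore depends partly on how well dosing goes. Radiographic progression may be documented later in patients with delays, for reasons unrelated to the tumor. That matters somewhat because the efficacy data are meant to inform a phase II design (2.3.1) and come from a small cohort spread over dose levels (13.1.3), where tolerability may differ. The six-month wording in 11.3.4 has the same weakness, since it treats course time and calendar time as one.

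**Working it through.** **Inputs from the documents.** Course length is 21 days (5.1.1). Scans fall at the end of courses 2, 5, 8, 11, 14, 18, 22, 26, 30 and 34 (Section 11). The toxicity-hold limit is 2 weeks, or 1 week if cytokine-related (Section 6).

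**Assumptions, not in the documents.** Time to progression is exponential with median 3, 6 or 9 months. The share of progressions found clinically when they occur is 0, 50 or 100%. A single hold falls before course 4, and a 6-week hold stands for a non-toxicity or surgery delay.

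**1. The plan's own figure.** On-time scan week = 3 × course number: weeks 6, 15, 24, 33, 42, 54, 66, 78, 90, 102. Course 8 ends at 8 × 21 = 168 days, and 168 / 30.4375 = 5.5 months. Course 11 ends at 231 days, 7.6 months. With on-time dosing, courses 2, 5 and 8 are indeed the routine scans in the first six months.

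**2. With delays.** Scan week = 3 × course number + all delay accrued before that course started.

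| Delay | Course 2 | Course 5 | Course 8 |
|---|---|---|---|
| None | 6 | 15 | 24 |
| One of 72 hours | 6 | 15.4 | 24.4 |
| One of 1 week | 6 | 16 | 25 |
| One of 2 weeks | 6 | 17 | 26 |
| One of 6 weeks (assumed) | 6 | 21 | 30 |
| 2 weeks before every course | 8 | 23 | 38 |

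One 2-week hold widens one interval from 9 to 11 weeks and moves all later scans by 2. In the extreme last row the intervals become 9 + 3 × 2 = 15 weeks, then 12 + 4 × 2 = 20.

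**3. The six-month wording.** Six months is 6 × 30.4375 / 7 = 26.1 weeks. Cumulative delay above 26.1 − 24 = 2.1 weeks puts the course 8 scan outside six months while 11.3.4 still names it.

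**4. Effect on recorded PFS.** Recorded time is the true time if progression is found clinically, otherwise the first scan at or after it. Each setting used 400,000 draws, with the same draws for every schedule, and every simulated patient had the delay. Progression after the last course was taken as found when it occurred. Mean PFS in weeks (increase over no delay):

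| Median; found clinically | No delay | One 2-week | One 6-week | 2 weeks every course |
|---|---|---|---|---|
| 3 months; 0% | 23.32 | 23.68 (+0.36) | 24.72 (+1.40) | 25.89 (+2.57) |
| 6 months; 0% | 42.12 | 42.35 (+0.23) | 43.02 (+0.90) | 45.14 (+3.02) |
| 9 months; 0% | 60.53 | 60.70 (+0.17) | 61.22 (+0.69) | 63.97 (+3.44) |
| 3 months; 50% | 21.04 | 21.22 (+0.18) | 21.74 (+0.70) | 22.32 (+1.28) |
| 6 months; 50% | 39.82 | 39.93 (+0.11) | 40.27 (+0.45) | 41.33 (+1.51) |
| 9 months; 50% | 58.40 | 58.49 (+0.09) | 58.75 (+0.35) | 60.12 (+1.72) |

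With all progression found clinically, every increase is 0.

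**5. The median.** A 6-month true median is week 26.1. With scan-only detection the on-time grid (24, 33) records week 33. One 2-week hold (26, 35) records 35, and one 6-week hold (21, 30) records 30. The observed median can therefore fall.

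**The case against.** Several points against the concern are sound.

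- **Holds are not open-ended in general.** A reader of 5.1.3 alone might infer that they are. Section 6 limits toxicity holds, 6.2.1 adds a 14-day rule for dose-limiting hematologic toxicity, and stopping treatment itself brings an MRI. What remains without a stated maximum is the non-toxicity delay and the surgery hold, plus the fact that a 2-week hold may recur.
- **Not every delay lengthens PFS.** A reader might infer that it does. Neurologic worsening counts as progression without a scheduled scan, death is an event, and an MRI is due at progression. A hold beginning after a scanned course does not move that course's own scan.
- **Confirmation of response is not a real conflict.** Section 9.2.1 asks for the confirming scan about three courses later, but Sections 11, 11.3.1 and 11.3.2 already work in weeks (9), and 9.2.1 is an image-upload instruction.
- **Materiality is low.** PFS is descriptive, with no comparator, test or threshold. Stratum 2 dose decisions rest on DLT counts (13.1.3).

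These narrow the point without removing it. The 72-hour allowance covers minor departures, and the documents do not say how it fits with the separate, unlimited sentence in 5.1.1. Nothing requires imaging during a hold, and no PFS rule handles a late scan.

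**Conclusion.** The point holds in a limited form. Because routine MRIs follow course number, a delayed course moves all later scans, and scan-detected progression in DIPG patients with delays can be recorded later. For a delayed patient, under scan-only detection, the expected shift in mean PFS is a fraction of a week for one permitted 2-week toxicity hold and about a week for one assumed 6-week hold. It reaches about 3 weeks only if every course slips by 2. Half-clinical detection roughly halves these figures.

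The sizes rest on assumed medians, detection shares and delay patterns; the documents give none of these. The averages apply to patients with the delay, so a cohort in which only some are delayed shifts less. The documents do not support a claim that DIPG PFS as a whole is materially inflated, or that its median must rise. This is a cheap improvement to a descriptive endpoint, and no primary objective is affected.

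**What to change.** In 9.2, Section 10 footnote E and Section 11, state the MRI schedule as weeks from first dose: 6, 15, 24, 33 and 42, then every 12 weeks to the end of therapy. Keep the 72-hour allowance and the scans at progression and completion. Add that a dosing delay or hold does not move the MRI. With on-time dosing the schedule is unchanged, and no dosing rule is touched.

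In 11.3.4, reconcile the six-month limit with the named courses, which can disagree once courses are delayed. Because that option bears on continuing therapy, the choice belongs to the study committee. Section 5 (72 hours) and 5.1.1 should likewise be reconciled on non-toxicity delays.

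**Cost.** This is a wording amendment. In patients with delays a scan may fall off a dosing visit and need separate scheduling or anesthesia. B-cell counts (footnote H) would no longer share the MRI visit unless re-timed as well. Stratum 2 was already accruing at this amendment, so patients already enrolled will have been scanned by course. Reporting actual scan dates alongside PFS in 13.3, or a sensitivity analysis for off-schedule scans, would make that visible.

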5.1.2 APX005M Infusion

APX005M is supplied in 20 mL (10 mg/mL) type 1 clear glass vials for intravenous injection. The target fill of each vial is 16.9 mL; the amount of APX005M that can be reliably extracted is 16.3 mL (163 mg)/vial. The calculated APX005M is prepared in 0.9% Sodium Chloride to a final volume of 50 mL, and administered as a 60 minute IV infusion. Sites should make every effort to

target infusion timing to be as close to 60 minutes as possible. A window between -5 minutes and +10 minutes is permitted (i.e., infusion time between 55 minutes and 70 minutes).

The APX005M infusion can be interrupted in the case of infusion related reaction/cytokine release syndrome (see Section 6.2.3). Once symptoms resolve, infusion should be restarted at 50% of the initial infusion rate (e.g., from 50 mL/hr to 25 mL/hr). If tolerated 10 minutes later it should be increased to the initial infusion rate. If symptoms recur with the increase in rate but the infusion is tolerated at the 50% rate, complete the infusion at the 50% rate without further attempts to increase the rate. It is recommended that the actual infusion time does not exceed 90 minutes. However, the infusion may last for a total of 2 hours in cases where the infusion is run at the 50% rate for the entire infusion. If infusion related reaction symptoms recur at the 50% rate despite decreased infusion rate and symptomatic treatment (Section 6.2.4) then permanently discontinue dosing.

For the infusion following one in which a patient developed infusion related reaction/cytokine release syndrome, initiate the infusion at the 50% rate. If the infusion is tolerated, increase the rate 10 minutes later to the 100% rate. If an infusion related reaction/cytokine release syndrome develops, interrupt the infusion and provide symptomatic care. Once symptoms resolve, restart the infusion at the 50% rate and do not increase the rate during the current infusion or for any future infusions. If infusion related reaction symptoms recur at the 50% rate despite decreased infusion rate and symptomatic treatment (Section 6.2.4), permanently discontinue dosing.

Subjects will be assigned a dose level at the time of enrollment. See section 5.1.1 for details of dose escalation schedule. See section 6.2 for dose modifications.

5.1.2.1 Pre-medication

Subjects are encouraged to have good pre-treatment hydration (good oral intake and/or IV fluids) prior to infusion. Subjects are encouraged to drink volume-increasing fluids (e.g., Gatorade, broth) for the remainder of the infusion day and maintain an adequate oral fluid intake for the first 24-48 hours after APX005M administration. Subjects must be premedicated prior to all APX005M infusions.

Approximately 30-60 minutes before the infusion of APX005M premedicate subjects with a regimen containing the following medications at the appropriate pediatric doses:

- Oral nonsteroidal anti-inflammatory drug (e.g., ibuprofen)
- Oral acetaminophen

Intravenous formulations of these medications (rather than oral) may be administered approximately 10 minutes prior to infusion. When the time between premedication and scheduled APX005M administration exceeds 4 hours, subjects may receive an additional course of premedication prior to APX005M administration.

The investigator may consider withholding anti-hypertensive medications on the day of APX005M administration if in the opinion of the investigator such action poses no risk to the subject.

It is strongly suggested subjects continue anti-pyretics (e.g., ibuprofen every 8 hours, alternating with acetaminophen every 8 hours x 3 doses at the appropriate pediatric dose) for 24 hours following each dose. If there is any concern regarding renal function or anticoagulation, consider

using a lower dose of ibuprofen or eliminating it from the regimen. If the patient continues to be symptomatic, consider continuing the regimen after the 3 doses as needed.

Subjects must be observed for at least 48 hours following the completion of the first 2 infusions of APX005M. Patients should be admitted to the hospital for 48 hours or must agree to stay within 1 hour driving distance from PBTC center for 48 hours following the first 2 infusions. If not admitted, subjects must be discharged into the company of a caregiver or healthcare provider who will continue to observe the subject for at least a 48-hour period following the first 2 infusions. Subjects and caregivers will both be provided with discharge instructions to contact the investigational site and/or seek medical care if appropriate. Subjects should be told to bring investigational site contact information and/or a copy of the informed consent document when seeking medical care from anyone other than the investigational site staff.

5.1.3 Criteria to Start Subsequent Courses

A course may be repeated every 3 weeks if the patient has at least stable disease, all drug-related toxicities return to baseline or \leq Grade 1 (excluding alopecia and Grade 2 fatigue) and has again met laboratory parameters as defined in Section 3.1.9. If a patient does not meet these parameters at the end of the treatment course then APX005M should be held until parameters meet the eligibility criteria.

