2.2.2 PBTC-051 Clinical Trial Experience

A total of 21 patients were enrolled on stratum 1. One patient was deemed ineligible after starting treatment on dose level 3 due to an incomplete eligibility assessment, leaving 20 eligible stratum 1 patients. Three were enrolled on dose level 1, 3 on dose level 2 and 14 on dose level 3. No dose-limiting toxicities (DLT) were noted in dose levels 1 or 2. Seven (6 evaluable) patients were subsequently enrolled on dose level 3 with no DLTs noted. Consequently, dose level 3 (0.6 mg/kg) was determined to be the RP2D. Seven additional (6 evaluable) patients were subsequently treated at dose level 3 in a dose expansion cohort to further define APX005M toxicities. Two DLTs were noted in this dose expansion cohort, for a total of 2 DLTs in 12 evaluable patients at the maximum dose level. Both DLTs were grade 3 infusion-related reactions. One occurred in cycle 1 and the other in cycle 2 of therapy. The most common adverse events recorded were lymphopenia (maximum grade 4), neutropenia (maximum grade 3), and leukopenia (maximum grade 4). The starting dose for the DIPG cohort (stratum 2) was chosen to be one dose level below the RP2D determined in stratum 1 as stated in Section 13.1.3 of the protocol document. This was driven by a concern that APX005M might be more toxic in DIPG patients, so we took a conservative yet also efficient approach for the stratum 2 safety study.

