3.1.9 Organ Function

Patients must have adequate organ and bone marrow function as defined below:

- Absolute Neutrophil Count (ANC) ≥ 1.0 x 10⁹ cells/ L
- Platelets ≥ 100 x 10⁹ cells/L (unsupported, defined as no platelet transfusion within 7 days)
- Hemoglobin ≥ 8 g/dL (may receive transfusions)
- Total bilirubin ≤ 1.5 times institutional upper limit of normal (ULN)
- AST(SGOT)/ALT(SGPT) ≤ 3 x institutional upper limit of normal (ULN)
- Albumin ≥ 3 g/dl
- Serum creatinine based on age/gender as noted in Table 1. Patients that do not meet the criteria in Table 1 but have a 24 hour Creatinine Clearance or GFR (radioisotope or iothalamate) ≥ 70 mL/min/1.73 m² are eligible.

Table 1

Serum Creatinine for age/gender		
Age	Maximum Serum Creatinine (mg/dL)	
	Male	Female
1 to < 2 years	0.6	0.6
2 to < 6 years	0.8	0.8
6 to < 10 years	1	1
10 to < 13 years	1.2	1.2
13 to < 16 years	1.5	1.4
≥ 16 years	1.7	1.4

The threshold creatinine values in this Table were derived from the Schwartz formula for estimating GFR (Schwartz et al. J. Peds, 106:522, 1985) utilizing child length and stature data published by the CDC.

- Cardiac Function:
 - Left Ventricular Ejection Fraction (LVEF) > 50%
 - ECG QTc ≤ 450 msec
- Pulmonary Function:
 - Oxygen saturation as measured by pulse oximetry is > 93% on room air and no evidence of dyspnea at rest

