5.2.1 Dose-Limiting Toxicities (DLT's)

- Any APX005M-related adverse event during the first 2 courses of therapy (6 weeks, 42 days) that leads to a dose reduction or results in the permanent cessation of therapy will be considered dose limiting. All dose modifications in all courses are to follow the guidelines provided in Section 6.2.
- Any APX005M-related adverse event during the first 2 courses of therapy that results in a delay of treatment > 2 weeks.

5.2.1.1 Non-hematologic dose limiting toxicity is defined as:

- Any grade 4 non-hematologic toxicity
- Any grade 3 non-hematologic toxicity with the exception of:
 - Grade 3 nausea and vomiting < 5 days
 - Grade 3 diarrhea responding to optimal medical treatment within 5 days
 - Grade 3 elevation of transaminases that returns to levels meeting eligibility criteria within 7 days of study drug interruption and does not recur upon restarting drug.
 - Grade 3 fever or infection of fewer than 5 days in duration

- Grade 3 hypophosphatemia, hypokalemia, hypocalcemia or hypomagnesemia that are asymptomatic and responsive to oral supplementation
- Grade ≥ 3 cytokine release syndrome
- Toxicity related to treatment with APX005M which delays scheduled re-treatment for > 2 weeks, or >1 week for cytokine release related complications.

5.2.1.2 Hematologic dose limiting toxicity is defined as:

- Any grade 4 hematologic toxicity with the exception of lymphopenia
- Grade 3 neutropenia with fever
- Grade 3 thrombocytopenia on 2 separate days or requiring a platelet transfusion on 2 separate days within a 7 day period.

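### Lymphopenia is exempt from the grade 4 hematologic DLT but not from the re-treatment, discontinuation and delay rules, so Stratum 2 sites could classify the same event differently

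*Combined protocol and SAP*

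**What the plan says.** Five parts of the combined protocol and SAP bear on this.

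- **DLT by grade (5.2.1.2).** The list includes "Any grade 4 hematologic toxicity with the exception of lymphopenia". This is the only place where lymphopenia is exempted from anything.
- **DLT by consequence (the general bullets of 5.2.1).** An APX005M-related event in courses 1-2 is dose limiting if it leads to dose reduction or permanent cessation. So is "Any APX005M-related adverse event during the first 2 courses of therapy that results in a delay of treatment > 2 weeks". Neither bullet mentions lymphopenia.
- **Re-treatment (5.1.3).** The patient needs "at least stable disease, all drug-related toxicities return to baseline or" grade 1 or less, "excluding alopecia and Grade 2 fatigue) and has again met laboratory parameters as defined in Section 3.1.9". Drug is otherwise held until the entry criteria are satisfied.
- **Discontinuation (opening of Section 6).** The rule covers "Any subject who fails to recover from a disease or treatment-related toxicity to baseline or" grade 1 or less ("except alopecia and Grade 2 fatigue) within 2 weeks of scheduled retreatment"), with a shorter limit of 1 week for cytokine-release toxicity. Such a subject should stop the drug.
- **Hematologic dose modification (6.2.1).** Any toxicity on the 5.2.1.2 list leads to the next lower dose level, and recovery is judged against the on-study parameters. Table 3 has rows for neutrophils and platelets only.

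Section 2.2 calls the lymphocyte fall reversible and believed to be a pharmacodynamic effect. Section 2.2.2 says of Stratum 1: "The most common adverse events recorded were lymphopenia (maximum grade 4), neutropenia (maximum grade 3), and leukopenia (maximum grade 4").

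**The concern.** The protocol treats a fall in lymphocytes as an expected action of the drug and spares it from the grade-based DLT. The rules that decide whether a patient gets the next dose do not clearly spare it, and they feed back into the DLT definition through delay and cessation.

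The event is unlikely to go unseen: lymphopenia is listed first among the most common events in Stratum 1, and the Section 10 calendar requires absolute lymphocyte counts weekly in courses 1-2.

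If one site holds and then stops drug for a low lymphocyte count while another re-treats on schedule, the first records a DLT and the second does not. The DLT count determines the MTD and RP2D, a primary objective, and drives the Stratum 2 cohort decisions in 13.1.3.

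**Working it through.** **Step 1. The literal chain.** Take a patient with a normal lymphocyte count at entry who develops drug-related grade 2-4 lymphopenia after course 1.

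1. Under 5.1.3 the toxicity is above grade 1, not at baseline and not one of the two exceptions, so course 2 is held.
2. Under Section 6, if it has not recovered within 2 weeks of the scheduled date, the drug should be discontinued.
3. Under the general bullets of 5.2.1, the cessation, or the delay beyond 2 weeks, is a DLT.
4. Under 11.1.1, a patient removed for toxicity after at least one dose is evaluable for the MTD, so the DLT enters the count.

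No text gives the 5.2.1.2 exemption precedence over steps 1 to 3.

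**Step 2. Timing.** Course 2 is due on day 1 + 21 = 22, so a delay of more than 2 weeks begins after day 22 + 14 = 36, inside the 42-day window. Course 3 is due on day 43. Section 5.2.2 extends dose finding to the start of a delayed course, so a delay past day 43 + 14 = 57 is also caught.

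**Step 3. The opposite reading.**

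- The last sentence of 5.1.3 ends the hold when the entry criteria are met. Section 3.1.9 ("Patients must have adequate organ and bone marrow function as defined below") lists neutrophils, platelets, hemoglobin, bilirubin, transaminases, albumin and creatinine, with no lymphocyte threshold.
- Section 6.2.1 tests recovery by on-study parameters, which again contain no lymphocyte limit.
- The first bullet of 5.2.1 sends dose modifications to 6.2, which assigns lymphopenia no action.

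On this reading the same patient receives course 2 on day 22 and has no DLT.

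**Step 4. Leukopenia.** It is not named in the 5.2.1.2 exemption. A related grade 4 leukopenia in the window is therefore a DLT on the text, even if driven by lymphocytes. The 6.2.1 paragraph then gives a dose reduction, while Table 3 has no leukopenia row. The table is narrower than the text above it.

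**Step 5. What one DLT does in Stratum 2.** Section 13.1.3 escalates from the starting level on 0/3, adds three patients on 1/3, and escalates on no more than 1/6. Two or more DLTs at that level lead to consideration of de-escalation. A cohort with one other DLT in six would escalate; one lymphopenia-delay DLT more makes 2/6, and de-escalation is considered.

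**Step 6. Illustration.** The Stratum 1 counts agree with each other: 21 - 1 = 20 = 3 + 3 + 14 eligible patients, and 6 + 6 = 12 evaluable at dose level 3 with 0 + 2 = 2 DLTs. Use 2/12 = 0.167 as the base rate. Let q be the probability that lymphopenia alone produces a DLT by delay or cessation. The documents do not give q, and it is taken as independent of other DLTs.

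- Total DLT probability: p = 1 - (1 - 2/12)(1 - q)
- Escalation: (1 - p)^3 + 3p(1 - p)^5
- At most 1 DLT in 6: (1 - p)^6 + 6p(1 - p)^5

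| q (assumed) | p | Escalate from a level | At most 1 in 6 |
|---|---|---|---|
| 0 | 0.167 | 0.780 | 0.737 |
| 0.05 | 0.208 | 0.691 | 0.635 |
| 0.10 | 0.250 | 0.600 | 0.534 |
| 0.20 | 0.333 | 0.428 | 0.351 |

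The row q = 0 is also the result if lymphopenia is exempt throughout.

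**The case against.** The strongest reply is that exempting an event by grade while counting it by consequence is coherent. Section 5.2.1.1 does the same: brief grade 3 nausea, fever and transaminase rises are excused by grade, yet a related toxicity that delays re-treatment by more than 2 weeks is a DLT. This stands. The DLT section alone is not self-contradictory; the difficulty lies in whether lymphopenia blocks re-treatment at all, where 5.1.3, 6 and 6.2.1 point in different directions.

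Second, 5.1.3 and Section 6 say drug should be held or discontinued, not that it must be, and Section 6.1 requires the study chair or co-chair to be told of dosage modifications. This also stands, but it is a partial safeguard: a site that re-treats on schedule makes no modification and has nothing to notify.

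Third, the effect may be rare. The fall is described as reversible, and because return to baseline suffices, patients already lymphopenic at entry are held only if they stay worse than baseline. This limits frequency, not the ambiguity.

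A reader might infer from the grade 4 leukopenia in 2.2.2 that Stratum 1 missed DLTs, since both recorded DLTs were infusion-related reactions. The documents do not support that. Section 7 records grade 3-4 events regardless of attribution, whereas 5.2 requires at least possible attribution and onset in the first two courses. Recorded grade 4 events with no matching DLT fit those rules.

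**Conclusion.** The point holds as an unresolved conflict between passages, of moderate importance. Two readings of the current text give opposite answers on whether lasting drug-related lymphopenia in courses 1-2 stops treatment and counts as a DLT. The practical exposure is in Stratum 2, which is still accruing and whose cohorts are small enough for one DLT to change a decision.

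The size is unknown. The fall in escalation probability from 0.78 to 0.69-0.43 rests on an assumed q of 5-20%, independence, and carrying the Stratum 1 rate of 2/12 over to Stratum 2. It shows sensitivity and is not an estimate.

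A reader might go further and conclude that 2/12 is understated or that the Stratum 1 RP2D is in doubt. The documents report no lymphopenia-driven delay, discontinuation or DLT. One or two added DLTs would give 3/12 (25%) or 4/12 (33%), but 13.1.2 states no numeric boundary after expansion to 12: the dose may be revised for excessive toxicity, and the RP2D rests on the totality of the data. No Stratum 1 decision is shown to have been affected.

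**What to change.** Reconcile 5.1.3, 5.2.1 (the general bullets and 5.2.1.2), the opening of Section 6, and 6.2.1. Each should give the same answer on whether lymphopenia, and leukopenia explained by lymphopenia, falls under four rules: re-treatment, discontinuation, delay or cessation as a DLT, and grade 4 as a DLT. State which passage governs if they appear to differ, and make Table 3 agree with the 6.2.1 paragraph above it. Which way to reconcile is for the study committee.

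Then apply the reconciled rule uniformly to existing Stratum 1 and Stratum 2 cases, checking window, attribution and delays, and record the result as a consistency check.

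The cost is about one sentence in each of the four places, an alignment of Table 3, and a review of data already held on 20 eligible Stratum 1 patients and those enrolled so far in Stratum 2. No new patients or measurements are needed.
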